9.3.3.3 Other variables

BOEHRINGER INGELHEIM Group of Companies**NIS Protocol Template****Page 20 of 30****Study number: 1484.0014****Document number: <insert>**

Smoking status will be identified at the patient level (where available). This will be observed at or prior to index diagnosis. Free-text searches will be explored, for presence of terms such as 'Tobacco' or 'Smoker' or 'Smoking'. Smoking status will be identified as one of these categories: Smoker, Ex-Smoker, non-smoker or unknown at index.

Alcohol consumption will be identified at the patient level (where available). This will be observed at or prior to index diagnosis. Free-text searches will be explored, for presence of terms such as 'used to drink daily or '1-2 week' or 'Never. Alcohol consumption status will be identified as one of three categories: Drinker, Ex-Drinker, non-Drinker or unknown at index.

9.4 DATA SOURCES

Founded in 2014, [REDACTED] is the first-to-market EHR data analytics provider in the retina space. [REDACTED] was founded by practicing retina specialists and data-analytics experts with the mission to provide real-world insights from analyzing retina practices' electronic health data. [REDACTED] database consists of de-identified data from EHRs from a geographically diverse panel of United States based private retina specialists. All data comes exclusively from private retina clinics; [REDACTED] not collect data from hospitals or institutions. [REDACTED]

[REDACTED] by an anonymized patient code assigned by the software vendor. Data from multiple sources are organized into the structured database residing in US-based cloud servers. Data is maintained in a secure, password-protected environment using standards associated with personal health information (PHI).

Data Completeness

The Electronic Medical or Health Record represents the entire patient file as maintained by the treating physician and practice with the exception of diagnostic images. Records are continuous regardless of the physician in the practice treating the patient but only to the extent the patient is treated in the same practice. The file is therefore a complete record of the treatments rendered through the practice.

Data completeness within an EHR is entirely dependent on the treating physician recording diagnostic, treatment and other information. Completion rates vary by data element and depend on the treating physician's opinion of the future utility of the information related to that patient's clinical presentation. Crucial visit information such as Procedures, drugs administered, diagnoses, payer, are required at every visit. Outcomes such as IOP and Visual Acuity are entered at 95+% of visits. Foveal thickness is recorded in approximately 30% of encounters where an OCT scan was taken. [REDACTED] neither adds nor removes information received. [REDACTED] receives the key treatment and outcomes information but does not receive every field contained in an EHR. [REDACTED] does extensive work with physicians analyzing their own data through clinical trials or other projects and have not found inconsistencies between the data and the physician's expectation of the data. This iterative process is an integral step in ensuring data accuracy and completeness of our data.

Capture of Concomitant Medications/Exposure

Medications administered by the treating retina specialist are identified using the structured field containing the relevant J-Code. Each drug is validated during the curation stage. Dates

BOEHRINGER INGELHEIM Group of Companies**NIS Protocol Template****Study number: 1484.0014****Page 21 of 30****Document number: <insert>**

of administration are the dates of the patient visit describing the treatment delivered. Disease coding is usually restricted to ocular diseases. Items like diabetes, hypertension or statin use must be identified through systemic medications that are received along with the associated procedure record. CPT codes are used in conjunction with J-Codes to enable [REDACTED] to identify both the procedure performed and all associated medications used. When entering all fields stated above physicians are also required to attach a laterality code. This allows [REDACTED] to confidently identify diseases, procedures, medications etc. by each specific eye. Anatomical outcomes are captured in our database through data entry fields and through free text fields. Physicians prefer to look at the images rather than a value, and [REDACTED] does not actively receive the images attached to the charts. [REDACTED] also receives information on fluid status (subretinal, intraretinal, sub-RPE, edema) which will include primarily present/not present but can also contain the severity level of the fluid. These are obtained and standardized from exam findings in free text fields, where physicians record information found during Optical Coherence Tomography (OCTs), Fluorescein angiographies, etc. Common descriptions of these types of entries are: "Subretinal fluid OD", "findings consistent with subretinal fluid".

9.5 STUDY SIZE

During the development of the protocol and while running the projects viability, a feasibility was run on the database identifying both patients and eyes with Dry AMD, and specifically with GA. This analysis was run using only ICD 10 codes and with the use of exam notes. Actual population counts are subject to change based on the dataset available at first data run, but all analysis will be based on the assumption that population sizes are relative to these numbers.

GEOGRAPHIC ATROPHY (PERIOD >=2016) (ICD 10 + Exam Notes)

# of Patients	72,718
# of Eyes	113,408
Avg months of follow-up	22
# of Patients with visits after 3 years	20,503
# of Eyes with visits after 3 years	31,647

9.6 DATA MANAGEMENT

[REDACTED] extracts data weekly from various EHR vendors where it is then stored on secure servers accessible only to [REDACTED]. [REDACTED] has multiple data warehouses where an iterative standardization is applied to the data to combine different sources and ensure data accuracy.

Once all data cleansing and standardizing has been performed by [REDACTED], a static dataset is created specifically for the study to ensure there will be no variation in data for its duration. At this point, data accessible for analysis through Microsoft SQL Server Management Studio 18 and the building of the patient population begins. Only after the study population is completed, and all metrics relevant to the analysis have been identified and extracted in aggregated form to excel for further analysis and output generation. The statistical software used for this analysis will be R – version 3.6.3, which will be used for any statistical analysis

BOEHRINGER INGELHEIM Group of Companies**NIS Protocol Template****Study number: 1484.0014****Page 22 of 30****Document number: <insert>**

performed (t-tests, chi-square test or proportion, Confidence intervals etc.). Graphs and tables will be generated using both R and Excel, where applicable.

No personal data will be provided to Boehringer Ingelheim

9.7 DATA ANALYSIS

9.7.1 Main analysis

All analysis will be performed individually on the study population(s). All study results will be provided in tables, and key findings will be highlighted and summarized. The analyses will be conducted at both the patient and patient eye level, as appropriate.

Analysis for objective:

To describe the characteristics* of patients with GA in at least one eye.

To describe characteristics* of the study eye and the fellow eye, at index diagnosis (i.e., proportion of patients with GA in the fellow eye, [REDACTED]

All demographics, and clinical characteristics will be summarized at the index diagnosis date (first diagnosis of GA in the study eye).

Characteristics include demographics, comorbidities, comedications (patient level).

And at eye level; AMD, GA, eCNV, other ocular comorbidities, functional parameters i.e. VA. As well as treatments administered prior to or at index.

Summary will include descriptive statistics; continuous variables will consist of mean (SD) and median (IQR) while categorical variables will be described using frequency and proportion. Absolute numbers (n) of the variables (either yes or patients as appropriate) will be always included in the description of the results.

Analysis for objective:

To evaluate and characterize the progression of newly diagnosed patients with GA during a 5-year follow-up period. To describe patients' characteristics, study eye and the fellow eye characteristics, [REDACTED]

[REDACTED] or progression of the GA lesion in the study eye. To evaluate changes in VA, to evaluate changes in the lesion location, and lesion size (where available).

Patients with GA will be analyzed as an overall group. Subgroups will be also analyzed separately: only GA, GA and wAMD, GA and other comorbidities, and bilateral GA at baseline.

Ocular comorbidities will also be tracked longitudinally (yearly) from index date (GA diagnosis in the database) to better understand the disease journey.

Disease progression will be analyzed at both patient and each individual eye level.

Progression to dry AMD, to GA and to wAMD will be assessed independently using time to event analysis, and also the rate of progression that is seen in the study (2nd, 3rd, 4th, and 5th) years. Bilateral GA eyes at baseline will be evaluated for progression to wAMD

BOEHRINGER INGELHEIM Group of Companies**NIS Protocol Template****Study number: 1484.0014****Page 23 of 30****Document number: <insert>**

For all time to event metrics, mean (SD), median and range will be summarized, while proportions will be summarized using N (%).

Kaplan Meier or Cox Hazard ratios may be applied when analyzing disease progression. Additionally, it will be determined how patients progress during the 1,2,3,4,5 years follow up according to the lesion location, and lesion size.

Analysis for objective:

To determine the occurrence of GA in the study eye during the study period (at the 12 (24, 36, 48, 60) month follow up period).

The calculation of the occurrence (new cases) of GA will be tracked against the overall number of patients included in the retinal specialist database (████████ database) in a time period (year) as the denominator initially.

The analysis to calculate the prevalent cases will include all patients with a GA diagnosis active in the database in the given time period in the numerator, and all patients included in the retinal specialist database (████████ database) will be used as the denominator initially.

Since, this analysis is referring to a population attending a retinal specialist during a given time period and therefore is not a general population-based estimates, in order to give a context to the data, the proportion of other common diagnosis in patients over 50 years or older attending the clinic in the same time period (e.g. diabetic macular edema, diabetic retinopathy, proliferative diabetic retinopathy, and wAMD) will be calculated. The denominator will be all patients attending to the retina specialist in the given time period using the age group category that is applicable in this study (50 years or older).

For the initial calculations, the look back period in 2015 will be used to discard patients with prevalence GA diagnosis in the subsequent years. prior diagnosis will be excluded and only new cases diagnosis in the time period will be considered in the numerator when calculating incidence.

The calculations will be conducted by calendar year, and absolute numbers (n) and correspondent percentage (%) will be provided. As a sub analysis, it will be evaluated if changes occurred after the third quarter of 2021, corresponding with the ██████████

An additional analysis will be made to extrapolate the prevalent results to a national – US-level. For that analysis, the prevalence of GA will be considering all patients seen by a retina specialist in the given year. With this metric, estimation on a national level will be done using an estimation of all practicing US retina specialists.

When analyzing the rate of progression from dry AMD to GA, a conversion analysis will be done. This will include the overall rate of dry AMD eyes developing GA, along with a Kaplan Meier analysis assessing the rate of conversion over time. This analysis will track progression by month from diagnosis, censor any patient at the final visit in the database, and identify the incident GA diagnosis as an event.

Analysis for objectives:

To evaluate patients' management (i.e. patients visits and procedures) over the study period.

BOEHRINGER INGELHEIM Group of Companies**NIS Protocol Template****Page 24 of 30****Study number: 1484.0014****Document number: <insert>****Patients' management**

All visits, treatment, checkups, procedures, and other will be summarized across the duration of the study time frame as well as between the index diagnosis and at the 12 (24, 36, 48, 60) month follow up period.

An additional sub analysis will be conducted to evaluate the changes in the frequency of patients visits or procedures, checkups, after the third quarter of 2021 and after [REDACTED].

Summary will include descriptive statistics; continuous variables will be described by absolute numbers, the mean (SD), median and range, while categorical variables will be described using frequency and proportion. Absolute numbers (n), and correspondent percentage (%) of the variables (either eyes or patients as appropriate) will be always included in the description of the results.

Analysis for objective:

To describe and compare patients' characteristics in different progression subgroups (i.e. those that develop eCNV/those that not), of the overall GA population.

The following groups will be evaluated to better understand progression:

1. Patients that [REDACTED]

vs. those that do not in the 1, 2, 3, 4 and 5 years of follow up period.

2. Patients that [REDACTED]

vs. those that do not in the 1, 2, 3, 4 and 5 years of follow up period.

3. Patients with subfoveal lesion location vs. those with extrafoveal lesion location.

For this subgroup of patient's characteristics will be described and compared.

Subgroups will be compared against one another to identify any differences in populations leading to progression. The characteristics will be extracted at the time of assignation to the group i.e. patient do not [REDACTED] in year one is contributing with his characteristics extracted at year 1 to the group (no progressors), that patient [REDACTED] at year 5 is contributing with his characteristics extracted at year 5 to the progressor group.

Summary will include descriptive statistics; continuous variables will be described by absolute numbers, the mean (SD), median and range, while categorical variables will be described using frequency and proportion. For discrete demographics or clinical characteristics, chi-squared test of proportion will be done to assess meaningful difference (standardized mean difference SMD may be used as an alternative), while continuous variables will be analyzed using SMD. Following univariate analysis on each metric, a multivariate logistic regression model will be run including relevant metrics identified in the univariate analysis.

Additional information on the analysis is described below:**Patient Demographics (at index and follow up):**

BOEHRINGER INGELHEIM Group of Companies**NIS Protocol Template****Page 25 of 30****Study number: 1484.0014****Document number: <insert>**

N (%); Age, gender, region; Bilateral status, other eye related diagnosis in study and fellow eye; Distribution by months of follow up; Concomitant illnesses (diabetes, cataract, etc.); Lesion location and size (along with % capture rate)

Progression : Progression of GA over time; Fellow eye AMD status; [REDACTED] (study and fellow eye) Mean (median/IQR) time to conversion; Conversion to GA (fellow eye) Mean (median/IQR) time to conversion; Proportion of patients with wAMD and GA (N, %)

[figure not shown]
Treatment Characteristics (follow up): Number of visits over time; Number of treatments over time, Mean (median) time to study treatment; Type of treatment – Anti-VEGF, Laser, Combination, Mean (median) time on therapy

New cases occurrence and prevalent cases of GA (stratified by index year): N (%)

- Age, gender
- Distribution by months of follow up
- Calculation to the % of patients attending the retinal specialist over the same time period for other retinal conditions i.e. wAMD, DR, dry AMD or DME.

Visual Acuity Outcomes

N (% capture rate); Mean (median) VA at index; Mean (median) VA at month 12; Change in VA from index to the different follow up times, VA distribution by buckets, Change in VA based on progression dates

BOEHRINGER INGELHEIM Group of Companies**NIS Protocol Template****Study number: 1484.0014****Page 26 of 30****Document number: <insert>****9.7.3 Safety Analysis**

There will be no safety analysis performed in this study

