9. RESEARCH METHODS

9.1 STUDY DESIGN

This is an observational cohort study based on existing data.

BOEHRINGER INGELHEIM Group of Companies**NIS Protocol Template****Study number: 1484.0014****Page 12 of 30****Document number: <insert>****9.1.1 Study population**

Study inclusion criteria: All patients ≥ 50 years, with a GA diagnosis in at least one eye, including in the [REDACTED] database identified during the study period (January 2015 to April 2023).

Exclusion criteria: Patients without the information of laterality will be excluded.

No other exclusion criteria are applied for the identification of the study population and description of the patients and eye at baseline.

Additional note:

For certain analysis the patient population will be restricted to those with at least 12, 24, 36, 48, or 60 months of history following diagnosis of GA. For the analysis requiring a VA reading, a restriction to those patients with valid VA readings at the index diagnosis and the respective follow-up times will be applied.

For analysis estimating the size of the GA population relative to other retinal diseases, the same timeframe requirements that the study population will be applied. In this population, any patient in the database will be eligible, and the diagnosis of DME, DR or other conditions may be used for subgroup comparisons.

Primary Disease Definitions

In the [REDACTED] Database, retinal and other diseases are identified using the International Classification of Diseases (ICD), Tenth Revision, Clinical Modification. ICD 10 codes were launched in the USA in October 2015, and are the only version of ICD codes with adequate descriptions of GA and dry AMD severity. As such, only ICD 10 codes will be analyzed in this study and the study period defined above is directly related to the launch of ICD 10 plus a small buffer allowing for physician familiarity.

These codes are entered by the physician at patient visit, with an associated laterality. This, along with the ICD 10 laterality is used in combination to confirm in which eye the disease is occurring. For this study, a patient eye will be considered to have the study disease so long as there is an accompanying ICD code. The primary study diseases to be analyzed are dry AMD, GA and wAMD, and will be identified using the ICD codes in Table 1 below.

Table 1. Study disease definitions-codes.

Study Disease Definitions			
	Dry AMD*	Dry AMD with GA*	wAMD*

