NIS Protocol Template

Study number: 1484.0014

Page 17 of 30

Document number: <insert>

- **Increase in the size of GA lesion will be assessed over time.** The size of GA lesion will be further defined following feasibility of data availability, with the basis of the lesion size defined using text field extracts. An example of text entries available for classification are defined below. Note that any analysis involving lesion size will need to be run on a subset population where these data are available/documentated;
Small: “Non-Central Geographic Atrophy, Small.”;
Medium: “Moderate Geographic Atrophy (Juxtafoveal)”;
Large: “1.5 DD Central Geographic Atrophy, Large.”, “Central Geographic Atrophy, Large.”, “4+ Geographic Atrophy.”
- **Progression of GA by Visual Acuity**

Change in visual acuity over time will be tracked from the incident date of GA, and assessed on a yearly basis in order to track the progression of GA over time. In this study, visual acuity will be defined as follows:

[REDACTED] receives VA data from Snellen charts in over 98% of cases, with some other types (ex. Jaeger, charts) in the remainder. There are no instances of ETDRS being received since all data are coming from private retina clinics. All VA entries are standardized and converted to LogMAR for reporting purposes. [REDACTED] standard output for VA is in the form of [REDACTED]

[REDACTED] will only compare VA results of a patient if vision is taken by the same measurement method; i.e., if a patient has their vision recorded using a DCC measurement at index diagnosis, for the remainder of the study, only DCC measurements will be accepted for comparison. This is done to ensure that any change in VA is due to actual change in the patients' vision, and not due to them taking a different vision test. Further, where DCC is not available for VA, any other measurements will be used, ensuring the same type of measurement will be used for the same eye to estimate the changes over time. The ranking order for measurement types is DCC ->NCC ->PH ->DSc ->NSc.

When capturing VA at different time points of interest, a buffer is allowed on either side of the date to increase the chances of each eye coming in for a visit. Should an eye have 2 readings inside the buffer window, the reading closest to the date of interest is taken. The buffers are proposed as follows:

- Index Diagnosis: +/- 30 days
- Follow up reading at Month 6, 12, or 18: +/- 30 days

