9.3.3 Covariates

9.3.3.1 Demographic Characteristics: The demographic variables below are identified at the patient eye level and will be used to describe the demographic characteristics throughout the analysis. These demographic characteristics will be analyzed at the index diagnosis, unless specified elsewhere.

Age: will be calculated based on DOB from index diagnosis (incident visit).

Sex: identified at index diagnosis, or other visits if not specified.

Diagnosis year: Identified as the calendar year of the index diagnosis.

Months of History: will be defined as the time from index diagnosis to their last record in the database.

Incident Visit: The first visit in the database where one of the study diseases is identified, per eye. This may include Dry AMD, GA and/or wAMD. At incident visits all clinical characteristics, ocular comorbidities, etc. will be also captured.

Prevalent Visit: The first visit during a time period of interest where one of the study diseases is identified, per eye. This may include Dry AMD, GA and/or wAMD. This visit must not be the first diagnosis in the entire patient history. At prevalent visits changes in the clinical

BOEHRINGER INGELHEIM Group of Companies**NIS Protocol Template****Study number: 1484.0014****Page 19 of 30****Document number: <insert>**

characteristics, ocular comorbidities will be captured and described based on the first prevalent visit per calendar year.

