As an overall limitation of the dataset, Data in the EHR is recorded by the physician or scribe under the direction of the physician. Physicians do not tend to enter data that is not directly relevant to the patient's current condition and tend not to enter null information. There is no real time validation of the information entered during the encounter either in terms of completeness or accuracy. However, ██████████ works extensively with the physicians providing analysis of their own data. As such, this is a crucial step in the data validation process, as physicians analyzing their own data over the years has provided insights on better coding, data entry and completeness. This limitation will affect the covariates related to comorbidities outside of retina. The current workaround is to use the systemic medications list provided to identify the treatment of these comorbidities (diabetes, hypertension etc.). However, this field also comes with its own limitation of relying on the physician/patient to provide an accurate summary of each patient's medication list.

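### No post-index window separates fellow-eye GA already present but coded late from new disease, so early fellow-eye conversion can be overstated

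*Combined protocol and SAP*

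**What the plan says.** Section 9.7.1 sets the baseline date: "All demographics, and clinical characteristics will be summarized at the index diagnosis date (first diagnosis of GA in the study eye". The eye-level items are then listed: "And at eye level; AMD, GA, eCNV, other ocular comorbidities, functional parameters i.e. VA". Section 9.3.3.1 ties capture to the visit: "At incident visits all clinical characteristics, ocular comorbidities, etc. will be also captured". Under section 9.1.1 no confirmation is needed: "a patient eye will be considered to have the study disease so long as there is an accompanying ICD code".

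Section 9.1.1 also makes the first eye coded with GA the study eye. The choice is random when a patient is bilaterally diagnosed, and no interval is given for what counts as bilateral. Section 9.3.2.1 lists new GA in the fellow eye as a progression endpoint. Section 9.7.1 analyses progression to GA and to wAMD as time to event and by yearly rates, and treats bilateral GA at baseline as a separate subgroup. Section 9.3.2.2 assumes that both eyes are assessed at every visit.

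The only window around index is "Index Diagnosis: +/- 30 days", and it is written for visual acuity: "When capturing VA at different time points of interest, a buffer is allowed on either side of the date". Treatments look backwards: "As well as treatments administered prior to or at index". The visible text states no blanking period, confirmation rule or minimum gap between index and a counted conversion.

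**The concern.** A patient may have GA in both eyes at the index visit while only one eye is coded that day. The coded eye becomes the study eye. Because both eyes are taken as assessed, the uncoded fellow eye is read as free of GA. When its code appears at a later visit, the plan has no rule to tell late recording from new disease, and the eye counts as a conversion.

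Each such eye does damage twice: it is missing from bilateral GA at baseline and it is added to fellow-eye conversions. The added events fall soon after index. They raise the early part of the time-to-event curve, which carries them forward into later years, and they shorten the mean and median time to conversion that section 9.7.1 asks for. They also move patients between the baseline subgroups and between the progressor and non-progressor groups. Fellow-eye conversion and the state of the fellow eye at index are both primary objectives in section 8.

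**Working it through.** The protocol states no conversion rate for this database and no late-coding share, so there is no planned figure to reproduce. The check has three steps.

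**1. Trace the rules for a fellow eye with GA present at index but coded at the next visit.**
- Study eye: the other eye, because it was coded first (9.1.1).
- Fellow-eye status at index: no GA code on or before that date, so no GA (9.1.1, 9.7.1).
- Next visit: one GA code, so disease is established (9.1.1).
- Outcome: a fellow-eye GA event at that visit (9.3.2.1, 9.7.1).
- Rules that could remove it: none visible. The minimum follow-up restrictions in 9.1.1 select patients by length of record and leave early codes in place.

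Look-back does not help here. The study eye is the first eye coded, so the fellow eye has no earlier GA code to find. The gap lies after index.

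**2. How many patients could be affected.** Section 9.5 (ICD-10 plus exam notes, from 2016) gives 113,408 GA eyes in 72,718 patients. Each patient contributes one or two eyes, so:

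patients with both eyes affected at some time = 113,408 − 72,718 = 40,690

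40,690 / 72,718 = 56.0%

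This is a ceiling on the exposed group, not an estimate of bias. It includes patients coded in both eyes at index and patients whose second eye truly developed GA later. It also uses exam notes, whereas the study definition uses ICD codes.

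**3. How the distortion behaves, under assumed inputs.** Let p be the true risk of conversion and q the share of eyes counted at risk that already had GA at index but were coded shortly afterwards. Then:

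observed risk = q + (1 − q) × p

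The documents give neither p nor q. Assume a one-year p of 2% to 10% and q of 1% to 5%:

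| p (1 year) | q = 1% | q = 2% | q = 5% |
|---|---|---|---|
| 2% | 3.0% | 4.0% | 6.9% |
| 5% | 6.0% | 6.9% | 9.8% |
| 10% | 10.9% | 11.8% | 14.5% |

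The extremes are 0.01 + 0.99 × 0.10 = 0.109, a ratio of 1.09, and 0.05 + 0.95 × 0.02 = 0.069, a ratio of 3.45.

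At five years with constant annual risk, true risk is 1 − (1 − p)^5:
- p = 10%, q = 1%: true 0.4095, observed 0.01 + 0.99 × 0.4095 = 0.4154, ratio 1.01.
- p = 2%, q = 5%: true 0.0961, observed 0.05 + 0.95 × 0.0961 = 0.1413, ratio 1.47.

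The direction and the concentration in the early period follow from the definitions. The sizes follow only from the assumed p and q.

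**The case against.** The case against a stronger claim is good on several counts.

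- **Coding completeness.** Section 9.9 says "Physicians do not tend to enter data that is not directly relevant", and a reader might infer that retina specialists leave GA or wAMD uncoded. The same paragraph confines that limitation to comorbidities outside the retina. Section 9.4 says diagnoses are required at every visit and that laterality must be attached. This stands: the documents do not show that late coding of GA occurs. What remains is that 9.4 also makes completeness depend entirely on the treating physician, and a required diagnosis is not the same as every diagnosis in both eyes.
- **Look-back.** A reader might infer that disease coded before index is ignored. Sections 9.1.1 and 9.3.3.1 define the incident visit over the whole history of the eye, so that reading largely fails. A clarifying sentence is enough.
- **wAMD.** A reader might infer that the same flaw is established for wAMD. The first primary-outcome item in 9.3.2.1 and parts of 9.7.1 are redacted, and the codes appendix is a separate file, so a rule for wAMD cannot be excluded.
- **The visual acuity window.** Its absence for diagnosis codes is not an inconsistency. The buffer exists because an acuity reading may be missing near a target date, whereas the index diagnosis always has a visit.
- **The remedy.** A post-index window uses later information to define baseline and relabels some true early conversions. This also stands, and it is why the planned analysis should be kept beside the windowed ones.

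**Conclusion.** The point holds for fellow-eye GA. As written, GA already present at index but first coded afterwards counts as a conversion, which can overstate early fellow-eye conversion and understate bilateral GA at baseline. For wAMD it is a possibility only.

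It would go too far to say that the early conversion rate is shown to be inflated, or by how much. The 56% shows that the order and timing of the two codes could matter for many patients. The late-coding share is unknown, and the factors of 1.09 to 3.45 at one year and 1.01 to 1.47 at five years are illustrations under assumed inputs. The conclusion rests on the visible text and on some second eyes being coded after the index visit although already affected. The study's own data can test that second condition.

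**What to change.** Make two changes before the analysis is run.

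1. State that baseline GA and wAMD status of each eye uses all codes in that eye's history up to and including index.
2. Report the conversion analyses, both time to event and yearly rates, in three versions: as planned; with codes first entered within 30 days after index treated as present at baseline; and the same with 90 days. In the windowed versions, time at risk starts after the window, so eyes whose record ends inside it leave the risk set. Report the number of eyes reclassified and the number that leave. The 90-day version is needed because the protocol gives no visit interval, and the next visit may fall after day 30.

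The cost is one definition and two reruns on the static dataset described in section 9.6. The downside is that some true early conversions are relabelled as baseline disease. The side-by-side estimates show how much that matters: close agreement would indicate that late coding within these windows has little effect. A large difference would bound the effect of early codes without proving that all of them were late.
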